5.1 Outcomes

5.1.1 Primary outcome

The primary outcome is change in physical function at 24 weeks as measured by the modified physical performance test (mPPT); a continuous outcome ranging from 0 (completely impaired) to 36 (full functional capacity).

5.1.2 Secondary outcomes

Deviation from the published protocol and trial registry

The order of the secondary outcomes will be presented as listed here, which has been modified compared to trial registry and protocol. This order is presented to ensure presentation of data in the order of relevance to the primary outcome.

Reported secondary outcomes

Change in mPPT between baseline and 12 weeks will be a secondary outcome.

Change in the following variables between baseline and 12 weeks (where available), and between baseline and 24 weeks, will be considered secondary outcomes:

	Week 12	Week 24	Categorical	Continous
KEY SECONDARY OUTCOMES				
HbA1c (mmol/l, %)	X	X		X
Weight (kg)	X	X		X
BMI (kg/m²)	X	X		X
DXA assesed body composition - total fat mass (kg), fat mass percentage (%), lean mass (kg), lean mass percentage (%)	X	X		X
MRI assessed absolute values will be reported for left ventricular end-diastolic volume (LVEDV) (mL), and LV mass (g). LV mass/LVEDV will be reported as a measure of concentricity. LVEDV and LV values indexed to body surface area will also be reported at baseline only.		X		X
VO ₂ peak – as absolute value (ml), relative to body weight (ml/kg) and relative to lean mass (ml/kg)	Х	X		X
Strength - quadriceps strength (Nm at 60°[isokinetic], 90° [isometric and isokinetic] and 120º[isokinetic] - reported as absolute (Nm), relative to body weight (Nm/kg) and relative to lean mass (Nm/kg) values. Bicep strength (repetitions) will also be reported.	Х	Х		Х
PROM - WHO Disability Assessment Schedule 2.0	Х	X		Х
OTHER SECONDARY OUTCOMES				
Other objective measures of function, fitness and strength	De Nieri	100000	100000000000000000000000000000000000000	
Short physical performance battery (SPPB)	X	X	X	X
Resting heart rate (beats/minute)	X	X		X
Handgrip strength (kg)	X	X		X
Body composition and muscle outcomes			Parling Name	
DXA outcomes – appendicular (arms and legs) lean mass (kg), bone mineral density (T-score), total bone mineral density (g/m²), total bone mass (kg)	Х	X		Х
Waist circumference (cm), neck circumference (cm)	X	X		X
Muscle ultrasonography - muscle cross-sectional area (cm²), muscle and subcutaneous fat thickness (cm), fibre angle pennation and echo intensity	Х	X		X
Resting metabolical rate (kcal/day)	Х	X		X
Main CMR and Echo measures	The state of the s	197 B. 18		
MRI - LV ejection fraction (%)		X		X
Echo - Diastolic transmitral flow velocities, E/A ratio and		X		X
early diastolic mitral annular velocities (e') to estimate LV filling pressures		^		^
Accelerometer-based physical activity measures and sleep				
Ambulatory activity (steps/day), overall acceleration (mg), intensity gradient and most active continious 10 and 30 minutes (mg)	Х	Х		X
Time spent sedentary (mins.day), and in light (mins/day), and moderate to vigorous physical activity (≥ 1 minute bouts) (mins/day)	X	X		X

Sleep window (mins/night), sleep duration (mins/night),	Х	Х		X
sleep efficiency (%), sleep midpoint variability				
Cardio-metabolic-renal indicators				
Systolic and diastolic blood pressure (mmHg) and heart rate (beats/min)	Х	Х		X
Cinical cardiometabolic biomarkers - fasting glucose (mmol/l), fasting insulin (mU/L), HOMA-IR, total cholesterol (mml/l), HDL (mmol/l), LDL (mmol/l) and triglycerides (mmol/l), C-reactive protein (mmol/l) NTproBNP (pg/ml)	X	X		X
Renal function - estimated glomerular filtration rate (eGFR) and urine albumin-to-creatinine ratio	Х	Х		X
Dietary variables				
Total energy (kcal/day) and macronutrients (g/day) (protein, carbohydrates, lipids)	X	Х		X
Food cravings – Control of Eating Questionnaire (CoEQ, VAS), Appetite Visual Analogue Scale (VAS)		X		X
Patient reported outcomes (PROMS)				
Hospital Anxiety and Depression Scale Questionnaire (HADS), Diabetes Distress Scale, mMRC Dyspnoea Scale, the European QoL-5 Dimensions (EQ-5D)(including VAS), General Practice Physical Activity Questionnaire (GP-PAQ)	X	X	X	X

5.2 Analysis methods

5.2.1 Deviations from the published protocol

A brief analysis plan was reported in the published protocol (Sargeant et al. 2024). The analysis plan described below is intended to supersede the published protocol. In particular, greater detail is provided on the sub-group analysis and missing data. The order of outcomes has been rearranged (as described in section 5.1.2). Select outcomes (MRI- derived intra- and inter-organ adiposity, cardiac strain parameters and aortic distensibility) that were described in the study protocol and/or trial registries but are omitted from this SAP. This is to avoid multiplicity in secondary outcomes and retain a focus on clinical parameters linked to the primary outcome. Additional exploratory outcomes will be saved for sub-analyses. We have also revised the stratification criteria for age (from 65 years to 70 years) to reflect older than anticipated population at recruitment with functional status also added as a stratification factor for the sensitivity analysis, reflecting the focus of the trial and primary outcome.

5.2.2 Analysis of the primary and secondary outcomes

Primary outcome

The mean and SD of mPPT will be calculated at baseline, by randomised group. Mean and SD of the change values will be reported between baseline and 12 weeks and between baseline and 24 weeks. The outcome at 24 weeks is primary.

For the primary outcome, the 97.5% confidence intervals and p-values for the comparison of each intervention group with the control group will be derived from a linear regression model with change in

mPPT as the dependant variable and randomisation group included as a fixed factor. Baseline mPPT value, randomisation stratification variables (sex, ethnicity, background medications) and age will be included as covariates. It is anticipated the primary outcome will be normally distributed. This will be inspected and alternative distributions will be considered where appropriate. P < 0.025 will be considered significant. The adjusted intervention effect (intervention vs control) will be used to interpret results.

Secondary outcomes

Secondary outcomes that are changes in continuous variables between baseline and either 12 or 24 weeks will be analysed using the same method as the primary outcome. However, secondary outcomes will be reported with 95% confidence intervals. P values will not be reported for secondary outcomes; results for the intervention effect that do not cross the null will interpreted as significant. Binary variables will be analysed using logistic regression.

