1.3 Primary hypotheses

- H₀: DAPA, alone and in combination with exercise training, will not improve physical function compared with matched diet-induced weight loss.
- H₁: DAPA, alone and in combination with exercise training, will improve physical function compared with matched diet-induced weight loss, with greater improvements in the combined therapy group.

2 Methods

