2.3 Sample size

To detect a clinically meaningful two-unit difference in the primary outcome (mPPT), with an SD of 2.4 units, 90% power and an alpha error rate of 0.025, 38 participants per group were required to complete the trial.

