5.2.8 Multiplicity

Since there are 2 primary comparisons, 97.5% (rather than 95%) confidence intervals will be reported for the primary outcome. All other secondary outcomes will be reported with 95% confidence intervals.

No formal corrections will be made to account for the large number of secondary outcomes and comparisons that will be presented. However, p-values for secondary outcomes will not be reported, and interpretation of the effects and confidence intervals will be made with caution, recognising the potential for chance findings among the multiplicity of outcomes and comparisons.

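### The fixed P < 0.025 rule for the two primary comparisons is valid but needlessly conservative; a Holm procedure would gain power for little more than a change of wording

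*SAP*

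**What the plan says.** The SAP sets up two separate superiority comparisons, DAPA versus diet control and DAPA+EX versus diet control (section 2.4).

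- **Decision rule (5.2.2):** "P < 0.025 will be considered significant", applied to each comparison whatever the result of the other.
- **Intervals (3.1 and 5.2.8):** "Since there are 2 primary comparisons, 97.5% (rather than 95%) confidence intervals will be reported for the primary outcome".
- **Sample size (2.3):** "To detect a clinically meaningful two-unit difference in the primary outcome (mPPT), with an SD of 2.4 units", with "90% power and an alpha error rate of 0.025, 38 participants per group were required to complete the trial". The section does not say whether the power refers to one comparison or to both.
- **Follow-on (5.2.7):** DAPA is compared with DAPA+EX if either primary p-value is below 0.025.

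No stepwise or other ordered testing procedure is specified.

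**The concern.** Splitting 5% equally between two tests and then holding both at 0.025 protects against a situation that no longer exists once one null hypothesis has been rejected. If DAPA+EX beats diet control at 0.025, at most one true null hypothesis can remain (barring an error already made), and that one can be tested at the full 0.05. The fixed rule does not use this. The cost falls on whichever arm has the weaker effect. Section 1.3 expects more improvement with the combination, so that arm is probably DAPA alone. A DAPA result with p between 0.025 and 0.05 would be called non-significant even after DAPA+EX had passed, although the familywise error rate does not require it.

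**Working it through.** **Inputs.** From the SAP: difference 2 units, SD 2.4, alpha 0.025, 38 completers per group (2.3); 1:1:1 allocation with a shared control (2.1), so the two test statistics correlate at 0.5. Two-sided testing is assumed because the SAP does not state sidedness; it is the choice that reproduces 38.

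**Step 1: the plan's own figure.** A two-sample t-test at two-sided 0.025 needs 38 per group and gives power 0.908. The normal approximation gives 2 × (2.241 + 1.282)² × 2.4² / 2² = 35.7, so 36. One-sided 0.025 gives only 31 (normal) or 32 (t). The stated 90% is therefore power for a single comparison.

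**Step 2: standardised effects.** SE = 2.4 × √(2/38) = 0.551. An effect of 2 has mean z = 2/0.551 = 3.63; an effect of 1.5 has 2.72. Critical values are c1 = 2.241 (two-sided 0.025) and c2 = 1.960 (two-sided 0.05).

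**Step 3: power for both comparisons.** Let P(a, b) be the bivariate normal probability (correlation 0.5) that the DAPA statistic exceeds a and the DAPA+EX statistic exceeds b.

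- Fixed rule: P(c1, c1).
- Holm: P(c1, c2) + P(c2, c1) − P(c1, c1).

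| Effects (DAPA, DAPA+EX) | Fixed | Holm |
|---|---|---|
| 2, 2 | 0.860 | 0.887 + 0.887 − 0.860 = 0.914 |
| 2, 2.5 (assumed) | 0.912 | 0.916 + 0.946 − 0.912 = 0.949 (unrounded terms) |

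Simulating three arms with pooled-variance t-tests (1,000,000 replicates) gives 0.851 and 0.908 for effects 2 and 2.

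**Step 4: power for DAPA alone.** The fixed rule gives Φ(mean z − c1). Holm adds P(c2, c1) − P(c1, c1), the chance that DAPA+EX passes at 0.025 while DAPA lies between the two thresholds.

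- DAPA 1.5, DAPA+EX 2 (1.5 assumed): fixed Φ(2.724 − 2.241) = 0.685; Holm 0.685 + 0.742 − 0.660 = 0.768 (unrounded terms). Simulation with t-tests: about 67% and 76%.
- DAPA 1, DAPA+EX 2 (1 assumed): simulation about 33% and 43%.

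**Step 5: familywise error under Holm.** If both nulls are true, an error needs the smaller p below 0.025, which has probability at most 2 × 0.025 = 0.05; the fixed rule has exactly the same error here (simulated 0.0465). If only one null is true, an error needs that p-value below 0.05, again at most 0.05.

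**Step 6: how often test and interval disagree.** Holm adds a rejection only when the larger p lies between 0.025 and 0.05, which is when its 97.5% interval includes 0. The gain in power for both comparisons is therefore also the probability of a mismatch: 0.908 − 0.851 = 0.057, about 6% of trials with effects 2 and 2.

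**The case against.** **The fixed rule is consistent and valid.** Sizing alpha, decision threshold and interval level all sit at 0.025 or 97.5%, so a result is significant exactly when its interval excludes 0. Holm gives that up. Preferring matching intervals to some extra power is a defensible choice. This stands in full, and it is why the point is an improvement and not a correction.

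**A stronger reading is tempting.** H1 in section 1.3 reads "DAPA, alone and in combination with exercise training, will improve physical function compared with matched diet-induced weight loss, with greater improvements" in the combined group. A reader might infer that both arms must beat diet control, so that the real power is 85% and the stated 90% is wrong. The SAP does not support this. Section 2.4 compares each arm separately, sections 3.1 and 5.2.8 speak of two primary comparisons, and section 5.2.7 acts on either one. Nowhere does success depend on both, so 90% per comparison is a legitimate target. If both were required, each could be tested at 0.05 with no multiplicity penalty (power for both 91.7%, normal approximation), and Holm would not be the natural remedy. The expectation that DAPA+EX exceeds DAPA is examined only conditionally, in section 5.2.7, and is not part of the primary decision rule.

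**The 85% is conditional.** It requires both true effects to be exactly 2 units. At 2 and 2.5, the direction H1 expects, the fixed rule already gives about 91% for both. Holm still gains there, but there is no shortfall below 90%.

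**The figures ignore covariates.** Section 5.2.2 adjusts for baseline mPPT, age and the stratifiers, and the SAP does not say whether SD 2.4 already allows for this. The absolute powers are therefore approximate. Holm's advantage over the fixed rule does not depend on them.

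**Conclusion.** A cheap improvement to a valid rule. At 38 per group and SD 2.4, Holm raises power for both comparisons by about 6 percentage points if both effects are 2 units (85% to 91%) and by about 4 if they are 2 and 2.5 (91% to 95%). For DAPA alone it adds about 9 points if the effects are 1.5 and 2 (67% to 76%). No participants are added and familywise error stays at or below 5%.

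These sizes rest on two-sided tests, a common SD of 2.4, 38 completers in every arm and no covariate adjustment; effects other than 2 units are illustrative. It should not be concluded that the sample size is wrong, that the trial is underpowered for its stated rule, or that the change is free: a significant second-step result may carry a 97.5% interval that includes 0.

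**What to change.** 1. **Section 5.2.2:** replace the fixed threshold with Holm: compare the smaller of the two primary p-values with 0.025 and, only if it passes, the larger with 0.05.
2. **Report Holm-adjusted p-values**, judged against 0.05: twice the smaller p for the first comparison, and the greater of that value and the larger raw p for the second (each capped at 1).
3. **Sections 3.1, 5.2.2 and 5.2.8:** keep the 97.5% intervals, say that significance follows Holm, and add a footnote that a comparison passing only at the second step may have a 97.5% interval that includes 0.
4. **Section 5.2.7:** the 0.025 trigger can stay, because Holm's first step is also 0.025. Say that it refers to unadjusted p-values.
5. **Optional, section 2.3:** state that the 90% power is per comparison.

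The cost is SAP wording and the footnote; no data collection or sample size changes. The amendment should be dated before anyone has seen primary outcome results by arm, since relaxing a threshold afterwards would not be credible.

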3.1 Confidence intervals and p-values

Since there are 2 primary comparisons (each intervention group vs diet control), the estimates of effect for the primary outcome will be reported with 97.5% confidence intervals. Secondary outcomes will be reported with 95% confidence intervals.

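### Section 5.2.2 labels a secondary effect significant whenever its unadjusted 95% interval excludes the null, which undoes the caution promised in section 5.2.8

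*SAP*

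**What the plan says.** **Primary outcome.** Section 5.2.8 gives the level and its reason: "Since there are 2 primary comparisons, 97.5% (rather than 95%) confidence intervals will be reported for the primary outcome". Section 5.2.2 adds the matching threshold: "P < 0.025 will be considered significant". Section 2.4 names the two comparisons, each intervention group against diet control.

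**Secondary outcomes, how they are reported.** Section 3.1: "Secondary outcomes will be reported with 95% confidence intervals". Section 5.2.2 repeats this, uses the same model as for the primary outcome (logistic regression for binary variables), and withholds p-values.

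**Secondary outcomes, how they are read.** Two sections answer this.

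- Section 5.2.2: "results for the intervention effect that do not cross the null will interpreted as significant".
- Section 5.2.8: "No formal corrections will be made to account for the large number of secondary outcomes and comparisons that will be presented". P-values are withheld there too. On how results will be read, it says: "interpretation of the effects and confidence intervals will be made with caution, recognising the potential for chance findings among the multiplicity of outcomes and comparisons".

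Section 5.1.2 makes change in mPPT at 12 weeks a secondary outcome and lists the others at 12 weeks (where measured) and 24 weeks. Section 5.2.7 may carry the section 5.2.2 approach over to a DAPA versus DAPA+EX comparison of the secondary outcomes, described as exploratory.

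**The concern.** A 95% interval that excludes the null is the same decision as two-sided p < 0.05 from the same model. Withholding the p-value therefore removes nothing if the interval is then turned into a verdict by a fixed rule. Section 5.2.8 relies on the absence of such verdicts: it accepts uncorrected intervals because they will be read as estimates that may include chance findings. The clause in section 5.2.2 takes that safeguard away.

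What is at stake is the wording of nearly every result other than the primary one. Two analysts could each follow the SAP faithfully and describe the same secondary interval differently, one as significant under section 5.2.2 and the other as an uncorrected estimate to be read cautiously under section 5.2.8.

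**Working it through.** **1. Primary threshold, checked against the sample size.** Section 2.3 gives a difference of 2, SD 2.4, power 90%, alpha 0.025 and 38 completers per group. It does not say whether alpha is one- or two-sided.

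- Two-sided, normal approximation: n = 2(z₀.₉₈₇₅ + z₀.₉₀)² × SD²/difference² = 2 × (2.2414 + 1.2816)² × 5.76/4 = 35.7, so 36 per group.
- Two-sided, exact t: power is 89.97% at 37 per group and 90.8% at 38, so 38 is reproduced.
- One-sided 0.025 gives 31 per group and does not reproduce 38.

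The primary test is therefore two-sided 0.025 per contrast, an even split of 0.05 over 2 contrasts.

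**2. What the secondary rule amounts to.** A 95% interval has critical value 1.96 and a two-sided error of 0.05 per contrast; a 97.5% interval has 2.24 and 0.025. The chance of at least one false label over the 2 contrasts of one outcome at one time point is:

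| Rule | If independent | Correlation 0.5 (shared control) |
|---|---|---|
| 97.5% interval (primary) | 1 − 0.975² = 4.94% | 4.6% |
| 95% interval (secondary label) | 1 − 0.95² = 9.75% | 9.1% |

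**3. The same instrument at two time points.** Take an mPPT contrast with p = 0.03. At 24 weeks 0.03 > 0.025, so it is not significant. At 12 weeks 0.03 < 0.05, so the 95% interval excludes zero and section 5.2.2 calls it significant. The model is the same.

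**4. How many intervals the rule covers.** Count from the table in section 5.1.2, variables × time points:

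| Group | Analyses |
|---|---|
| Key: HbA1c 2, weight 2, BMI 2, DXA 4×2, MRI 3×1, VO₂peak 3×2, strength (4 quadriceps tests × 3 scalings + biceps) × 2 = 26, WHODAS 2 | 51 |
| mPPT at 12 weeks | 1 |
| Other: function 6, body and muscle 24, MRI and echo 4, activity and sleep 24, blood pressure, biomarkers and renal 26, diet 10, patient-reported 12 | 106 |
| **Total** | **158** |

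158 × 2 contrasts = 316 intervals. If every null were true, the expected number of labels is 316 × 0.05 = 15.8, of which 51 × 2 × 0.05 = 5.1 are among the key outcomes. Correlation between outcomes does not change these expected counts.

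**5. Sensitivity to the count.** Counting heart rate again in the blood pressure line, and one more patient-reported score, adds 4 analyses: 162 × 2 = 324 intervals and 16.2 expected labels. At the other extreme, the 8 key lines taken as one variable each at 24 weeks give 8 × 2 = 16 intervals and 0.8 expected labels. The chance of at least one is then 1 − 0.95¹⁶ = 56% if independent, and lower if positively correlated.

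**6. Would 97.5% intervals cure it?** No. 316 × 0.025 = 7.9 labels would still be expected under the global null.

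**The case against.** The strongest reply is that the two sections can be read together: section 5.2.2 supplies a nominal label, and section 5.2.8 discloses that it is uncorrected and should be read cautiously. The disclosure is real, and it makes the unadjusted 95% intervals acceptable. It does not rescue the label. Section 5.2.2 states the label as a rule without qualification and does not refer to section 5.2.8, and an automatic verdict is not a cautious reading.

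Three stronger readings are tempting, and the SAP does not support them.

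- *That 95% for secondary outcomes is itself an error.* The 97.5% level divides the error rate over the two primary comparisons. The SAP claims no error control for secondary outcomes, so a different interval level is not a fault. The looser bar matters only because the label turns the interval into a test.
- *That the report will contain about 16 false claims.* That number needs every null to be true. Section 1.1 says this drug class is associated with weight loss and better glycaemic control, and one arm adds exercise training, so a global null is a worst case. Many analyses also rescale one measurement: the quadriceps tests alone supply 4 × 3 × 2 = 24 of the 51 key analyses.
- *That the third contrast raises this to 158 × 3 = 474 intervals and about 24 false labels.* Section 5.2.7 opens that contrast for secondary outcomes only after a primary contrast reaches p < 0.025 and DAPA and DAPA+EX also differ on the primary outcome. If no effects exist, the first condition alone is met at most about 5% of the time, so the figure combines incompatible assumptions. The comparison is also declared exploratory.

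It also stands that section 5.2.1 reports outcomes dropped to limit multiplicity, and that primary inference, models and estimates are untouched.

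**Conclusion.** The point holds as a conflict between two sections over how secondary results are to be described. Section 5.2.2 reinstates an uncorrected two-sided 0.05 test per outcome, time point and contrast; section 5.2.8 withholds p-values and promises caution because no correction is made. Both cannot be followed as written. The defect is the automatic label, not the intervals.

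The scale of about 16 labels in about 316 intervals, about 5 of them among key outcomes, rests on two assumptions: that no effect exists anywhere, and one reasonable way of splitting composite lines. It shows what the rule permits and is not a forecast. The conflict does not depend on the count. The sample size and the primary analysis are not affected.

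**What to change.** In section 5.2.2, delete the clause "results for the intervention effect that do not cross the null will interpreted as significant" and put in its place:

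> Secondary outcomes are reported as adjusted effect estimates (mean differences or odds ratios) with 95% CIs not adjusted for multiplicity; they will be interpreted as described in section 5.2.8, and no secondary result will be described as statistically significant on the basis of its CI excluding the null value.

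The wording refers to the null value rather than zero because binary outcomes are analysed by logistic regression, where the null odds ratio is 1. Apply the same wording to the exploratory DAPA versus DAPA+EX comparison in section 5.2.7.

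This does not require a testing hierarchy. If the sponsor wants formal secondary claims, that is a separate addition and would need named outcomes, a procedure, an alpha level and an allocation across the two contrasts.

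The cost is a change of SAP wording, with fewer secondary claims available. No data, model or estimate changes. It should be made before results are interpreted.
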